9.3.3 Covariates

Table 9.3.3:1 Covariates related to patient profile

	Data from Medical Charts	Data Measured at Study Visit
Age, gender, ethnicity.	X	
Height & weight (BMI auto-calculated) *	X	
Smoking history.	X	
Pulmonary function test - Spirometry # *	X	
Bronchodilator test # * (FEV ₁ increase, absolute values).	X	
Episodes of wheezing in exacerbations.	X	
COPD diagnosis (year)	X	

History of asthma (yes/no) and year of diagnose	X	
History of atopy (yes/no).	X	
Blood Eosinophilia (number of eosinophils and %) *	X	
Immunoglobulin E (Ig E) *	X	
Current COPD treatment (including ICS: start and stop dates, dose, reason) §	X	
History and details of Exacerbations (last 2 years).	X	
History of antibiotics and oral corticosteroids for COPD	X	
Comorbidities (COTE index)	X	
Concomitant medication.	X	
COPD GesEPOC 2017 phenotypes	X	
GOLD 2017 spirometric classifications (1, 2, 3, 4).	Auto-calculated	
GOLD 2017 patient groups (A, B, C, D).	Auto-calculated	
BODEx (BMI / % FEV ₁ / mMRC / severe Exacerbations)	Auto-calculated	
Breathlessness based on mMRC score.		X
QoL: CAT - COPD Assessment Test		X

* Last measure available

available in medical charts <12 months

§ Not including possible changes or new prescriptions done at study visit

The covariates will also be included as independent variables for multivariable analysis: COPD phenotypes, GOLD group, BODEx index, mMRC score and CAT – COPD Assessment Test.

9.4 DATA SOURCES

Data collection will be limited to those variables available in the medical records and data obtained / measured during the study visit (see Table [9.3.2.1:1](#) and Table [9:3:3: 1](#)) of selected patients.

CAT – COPD Assessment Test will be filled in by the patient following the user guide during the study visit and data will be entered electronically into the CRF system.

9.5 STUDY SIZE

Due to the descriptive design of the proposed non interventional study, a formal sample size calculation has not been performed based on statistical power and protection for type I error.

In previously published studies in usual clinical practice in primary care in Spain (4), 66% of patients are non-exacerbators and of these, 61% are treated with ICS, therefore approximately 40% of all patients are currently treated with ICS without having exacerbations in the prior year.

Assuming a sample size of 900 patients and 40% of the patients are treated with ICS at the study visit and did not have a moderate or severe COPD exacerbation in the prior year, the 95% confidence interval for this proportion would be between 36.8% (lower limit) and 43.2% (upper limit). To account for a 10% drop-out rate (patients with inconsistent, incomplete or missing data), the sample size becomes 1,000 patients.

Table 9.5:1 Scenario for estimated proportions by 95% CI

Scenario for estimated proportions by 95% confidence intervals (95% CI)

	1	2	3	4	5	6	
Expected proportion		0.4			0.5		
Lower and Upper limit of 95% CI	(0.37;0.43)	(0.368;0.432)	(0.365;0.435)	(0.47;0.53)	(0.468;0.532)	(0.465;0.535)	
Precision of estimation	0.03	0.032	0.035	0.03	0.032	0.035	
N (at final analysis)	1000	900	753	1042	938	784	
Dropout	10%	1112	1000	838	1159	1043	872

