9.3.2 Outcomes

9.3.2.1 Primary outcomes

The primary outcome is to describe the proportion of patients currently on ICS who did not have moderate/severe exacerbation in the year prior to the study visit.

Table 9.3.2.1:1 Variable related to primary outcome

	Data from Medical Charts	Data Measured at Study Visit
History and details of Exacerbations (last 1 year).	X	

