16. PRIMARY OUTCOMES

16.1 Primary Endpoint

The primary endpoint for a patient, currently on ICS, is absence or presence of moderate/severe exacerbation in the year prior to the study visit.

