16.1.3 Primary Analysis of Primary Endpoints

The primary analysis will consist of the proportion of patients, currently on ICS, who did not have or had moderate/severe exacerbation in the year prior to the study visit. The primary analysis will be performed for the FAS.

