16.1.3.1 Current treatment with ICS

Main variable will be presented according to the presence or not of moderate/severe exacerbations in the previous 365 days.

The use of ICS will be analyzed using number of patients in each category and percentages (absolute and relative frequencies) and 95% confidence intervals will be provided based on Wald's (Normal Approximation) method for each group. Percentages will be compared using Chi-Square test or Fisher's Exact test.

Logistic regression will be used to assess the independent contribution of clinical and demographic factors to the estimation of the proportion of patients with COPD who use ICS inadequately. First, univariate and second, multiple logistic regression (MLR) methods will be used to investigate the impact of the following explanatory covariates (patient and disease characteristics) on ICS use.

Potential covariates are:

- Age
- gender
- Smoking history
- Number of exacerbations in the previous year.
- History of asthma (yes/no)
- History of atopy (yes/no)
- COTE index
- COPD GesEPOC 2017 phenotype

Document: \\bcnfs02\general\Hdmgener\MEDICAL AFFAIRS 28.02.2017 actualizada\8. SRO ESTUDIOS\RESPIRATORIO\1237-0070 NIS OPTI\11 - Clinical Trial Report\SAP\SAP - V 1.0\SAP OPTI version1.0 29052019.docx

Author:

Version Number: 1.0

Version Date: [29MAY2019]

Template No.: RWI_TP_BIOS0013 Revision 1

Reference: RWI_WI_BIOS0015

Effective Date: 15Jun2018

Copyright © 2018 All rights reserved. The contents of this document are confidential and proprietary to Holdings Inc. and its subsidiaries. Unauthorized use, disclosure or reproduction is strictly prohibited.

- GOLD 2019 spirometric classifications (1, 2,3, 4)
- GOLD 2019 patient groups (A, B, C, D)
- mMRC score
- CAT - COPD Assessment Test

Backward selection procedures will be applied to generate the final MLR models which consider only covariates in the selection procedure with a p-value <0.1 in the corresponding univariate logistic regression analysis, using inadequate ICS use (yes/no) as response variable. A p-value <0.05 will be used for the covariates to stay in the model in a backward elimination step. Continuous variables can be replaced by categorical variables. Parameters estimated, exp(B) and C95% Wald Confidence Limits for OR will be presented.

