16.1.3.2 Inadequate use of ICS

As a part of main analysis, inadequate use of ICS will be presented as in the previous section 16.1.3.1. Current treatment with ICS. This analysis will be presented only for patients without exacerbations in the previous year. This cohort will be used because only patients without exacerbations can receive ICS without requiring it, which is, making an inappropriate use of the treatment.

Document: \\bcnfs02\general\Hdmgener\MEDICAL AFFAIRS 28.02.2017 actualizada\8. SRO ESTUDIOS\RESPIRATORIO\1237-0070 NIS OPT\11 - Clinical Trial Report\SAP\SAP - V 1.0\SAP OPTI version1.0 29052019.docx

Author:

Version Number: 1.0

Version Date: [29MAY2019]

Template No.: RWI_TP_BIOS0013 Revision 1

Reference: RWI_WI_BIOS0015

Effective Date: 15Jun2018

Copyright © 2018 All rights reserved. The contents of this document are confidential and proprietary to Holdings Inc. and its subsidiaries. Unauthorized use, disclosure or reproduction is strictly prohibited.

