20. TABLES AND FIGURES

20.1 Evaluability

Table 3. Evaluability criteria – Patients in the FAS

		Total
Total included patients (ENR)		
Evaluable patients	Evaluable patients (FAS)	
	Non-Evaluable patients	
Reasons for non-evaluable patients	Inclusion criteria 1	
	Inclusion criteria 2	

ICS Analysis Set (PICAS)		
Safety Analysis Set-ICS		
Safety Analysis Set- BI drug		

Table 4. Other protocol violations occurred in evaluable patients

		Total
Evaluable patients	Evaluable patients (FAS)	
Important protocol violations	ADR (serious or non-serious) or fatal event not notified to BI	
	Any other major or critical Non-Compliance detected during monitoring visit	

Table 5. Main stratification variables

		Total
Total evaluable (FAS)		
Current treatment on ICS	Total	
	No (Non - ICS treatment)	
	Yes (ICS treatment)	
	95% CI for current ICS treatment	
Moderate/severe exacerbations in the previous year	Total	
	No (Without Moderate/severe Exacerbations)	
	Yes (With Moderate/severe Exacerbations)	
	95% CI for presence of moderate/severe exacerbations in the previous year	
Inadequate use of ICS	Total	
	Adherent patients: Adequate use of ICS	

Document: \\bcnfs02\general\Hdmgener\MEDICAL AFFAIRS 28.02.2017 actualizada\8. SRO ESTUDIOS\RESPIRATORIO\1237-0070 NIS OPTI\11 - Clinical Trial Report\SAP\SAP - V 1.0\SAP OPTI version1.0 29052019.docx

Author:

Version Number: 1.0

Version Date: [29MAY2019]

Template No.: RWI_TP_BIOS0013 Revision 1

Reference: RWI_WI_BIOS0015

Effective Date: 15Jun2018

Copyright © 2018 All rights reserved. The contents of this document are confidential and proprietary to Holdings Inc. and its subsidiaries. Unauthorized use, disclosure or reproduction is strictly prohibited.

		Total
	Non-adherent patients: Inadequate use of ICS (use of ICS in patients without moderate/severe exacerbations in the previous year) 95% CI for non-adherent patients (inadequate use of ICS)	

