20.3 Endpoints

20.3.1 ICS treatment

Table 24. Current treatment on ICS according to the absence or presence of moderate/severe exacerbations in the year prior to the study visit.

ICS treatment	Moderate/severe Exacerbations in the previous year		Total
	No	Yes	
Total patients	N (100%)	N (100%)	N (100%)
Currently non treated with ICS	XXX (XX.X%) [95%CI: XX.X%-XX.X]	XXX (XX.X%) [95%CI: XX.X%-XX.X]	XXX (XX.X%) [95%CI: XX.X%-XX.X]
Currently treated with ICS	XXX (XX.X%) [95%CI: XX.X%-XX.X]	XXX (XX.X%) [95%CI: XX.X%-XX.X]	XXX (XX.X%) [95%CI: XX.X%-XX.X]

*Note: Percentages will be column percentages. Each percentage will correspond to percentage of patients currently treated with ICS, according to the presence of moderate/severe exacerbations in the previous year.

Table 25. Inadequate use of ICS (use of ICS without moderate/severe exacerbations in the previous year) according to clinical and demographic factors (univariate logistic regression analysis)

Variable	Category	Inadequate use of ICS	Odds-Ratio (OR)	p-value
Age	Cont (1 year)	n/N (%)		
Age (cat)	40-49 years	n/N (%)	(ref)	
	50-59 years	n/N (%)		
	60-69 years	n/N (%)		
	70-79 years	n/N (%)		
	80+ years	n/N (%)		

Document: \\bcnfs02\general\Hdmgener\MEDICAL AFFAIRS 28.02.2017 actualizada\8. SRO ESTUDIOS\RESPIRATORIO\1237-0070 NIS OPTI\11 - Clinical Trial Report\SAP\SAP - V 1.0\SAP OPTI version1.0 29052019.docx

Author:

Version Number: 1.0

Version Date: [29MAY2019]

Template No.: RWI_TP_BIOS0013 Revision 1

Reference: RWI_WI_BIOS0015

Effective Date: 15Jun2018

Copyright © 2018 All rights reserved. The contents of this document are confidential and proprietary to Holdings Inc. and its subsidiaries. Unauthorized use, disclosure or reproduction is strictly prohibited.

Variable	Category	Inadequate use of ICS	Odds-Ratio (OR)	p-value
Gender	Male Female		(ref)	
BMI cat	Underweight: BMI< 18.5 kg/m ² Normal weight: 18.5 kg/m ² ≤ BMI≤ 25 kg/m ² Overweight: 25 kg/m ² < BMI≤ 30 kg/m ² Obese: 30 kg/m ² <BMI≤ 35 kg/m ² Severely Obese: BMI> 35 kg/m ²		(ref)	
Smoking habit	Non-smoker Smoker Ex-smoker		(ref)	
History of asthma	No Yes		(ref)	
History of atopy	No Yes		(ref)	
BODEx Index (cat)	Class I Mild: BODEx 0-2 points Class II Moderate: BODEx 3-4 points Class III Serious: BODEx 5-6 points Class IV Very serious: BODEx 7-9 points		(ref)	
COTE Index (cat)	Low risk: COTE index <4 points High risk: COTE index ≥ 4 points.		(ref)	
Time since COPD diagnosis (cat)	0-2 years >2-5 years >5 years		(ref)	

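### The primary outcome is a share of ICS users, but the stated ±3.2-point precision is for a share of all patients, and Table 24 puts its confidence interval on the reverse percentage

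*Protocol*

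**What the plan says.** **Outcome.** Protocol 9.3.2.1 sets the primary outcome as the "proportion of patients currently on ICS who did not have moderate/severe exacerbation in the year prior to the study visit". Secondary outcome (a) in Protocol 9.3.2.2 is the same share for ICS users who did have an exacerbation. SAP 16.1 words it per patient: "The primary endpoint for a patient, currently on ICS, is absence or presence of moderate/severe exacerbation in the year prior to the study visit". SAP 16.1.3 repeats the direction: "The primary analysis will consist of the proportion of patients, currently on ICS, who did not have or had moderate/severe exacerbation". It assigns the analysis to the FAS.

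**Precision.** Protocol 9.5 multiplies 66% non-exacerbators by 61% ICS use among them to reach about 40% of all patients. It then gives an interval of 36.8% to 43.2%: "Assuming a sample size of 900 patients and 40% of the patients are treated with ICS at the study visit and did not have" an exacerbation in the prior year. SAP 4.2 repeats this and lists scenarios down to N=674 (±3.7 points).

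**Analysis.** SAP 16.1.3.1, which sits under the primary analysis, says: "Main variable will be presented according to the presence or not of moderate/severe exacerbations in the previous 365 days". It describes ICS use with Wald 95% intervals in each group. The columns of Table 24 are exacerbation no/yes, and its note reads: "Percentages will be column percentages. Each percentage will correspond to percentage of patients currently treated with ICS".

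**Other shells.** Tables 11 and 31 split exacerbation presence by ICS status but show no interval line. Table 5 has a row labelled "95% CI for non-adherent patients (inadequate use of ICS"), under the FAS total. SAP 16.1.3.2 restricts the inadequate-use analysis: "This analysis will be presented only for patients without exacerbations in the previous year".

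**The concern.** Three percentages can be formed from the same two-by-two table, and the plan uses a different one in each place:

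- Outcome definition: no exacerbation given ICS, with ICS users as the base.
- Study size: ICS and no exacerbation, with all patients as the base.
- Primary table: ICS given exacerbation status, with non-exacerbators or exacerbators as the base.

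The first asks how many ICS users are non-exacerbators. The third asks how many non-exacerbators are on ICS. These can differ by several points in either direction. A programmer following Table 24 would produce the third with its interval, and a reader of Protocol 9.5 would expect the second. Neither document says which percentage is primary, and the stated precision does not describe the outcome as worded. In a descriptive study, precision is the only justification given for the sample size, so it should refer to the primary quantity.

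**Working it through.** **Inputs.** From Protocol 9.5 and SAP 4.2: N=900 analysed; 66% non-exacerbators, hence 34% exacerbators; 61% ICS use among non-exacerbators. Two-sided 95% Wald interval, half-width 1.96 × √(p(1−p)/n). ICS use among exacerbators, x, is not in the documents and is varied below.

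**1. The plan's own figure.** Joint share: 0.66 × 0.61 = 0.4026. With p=0.40 and n=900, 1.96 × √(0.40 × 0.60/900) = 3.20 points, so 36.8% to 43.2%. Allowing for dropout, 900/0.90 = 1,000. Both figures reproduce, for a share of all patients.

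**2. Table 24, non-exacerbator column.** n = 0.66 × 900 = 594 and p = 0.61. Then 1.96 × √(0.61 × 0.39/594) = 3.92 points, so 57.1% to 64.9%.

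**3. The outcome as worded.** Expected number of ICS users: n = 900 × (0.4026 + 0.34x). Share without exacerbation: p = 0.4026/(0.4026 + 0.34x).

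| Assumed x | ICS users, n | p | Half-width (points) | p minus 61% (points) |
|---|---|---|---|---|
| 50% | 515 | 70.3% | 3.94 | +9.3 |
| 61% | 549 | 66.0% | 3.96 | +5.0 |
| 70% | 577 | 62.8% | 3.94 | +1.8 |
| 80% | 607 | 59.7% | 3.90 | −1.3 |
| 90% | 638 | 56.8% | 3.84 | −4.2 |

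The Table 24 figure and the outcome agree only when 0.4026 + 0.34x = 0.66, that is x = (0.66 − 0.4026)/0.34 = 0.757. The joint share of 40.3% is at least 56.8 − 40.3 = 16.5 points below the outcome across this range. The half-width exceeds the stated 3.20 by 0.64 (3.84 − 3.20) to 0.76 (3.96 − 3.20) points.

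**4. Wider assumptions.** At x=20%, n is about 424 and p = 0.4026/0.4706 = 85.6%, ±3.35. At x=100%, n is about 668 and p = 54.2%, ±3.78. The largest half-width at any x is 3.96 points. Even at x=100% the expected number of ICS users stays below 674, the smallest N in SAP Table 1, so no listed scenario covers the outcome as worded.

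**5. Does any shell print it with an interval?** Table 24 does not, because its percentages run within exacerbation columns. Tables 11 and 31 have the right direction but no interval line. The Table 5 row is the joint share (about 40%) if taken over the FAS, or ICS use among non-exacerbators (about 61%) if restricted as in SAP 16.1.3.2. Tables 28 to 30 are not in the text available and could not be checked.

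**The case against.** The best defence is that the outcome was meant as a joint share. SAP 16.1.3 runs the primary analysis on the FAS although SAP 6.3 defines a separate ICS-treated set, and Protocol 9.5 and SAP 4.2 say plainly that the 40% is of all patients. On that reading the precision is right, and the Table 5 row could carry the result. The wording of SAP 16.1 and the complementary secondary outcome (a) count against it: the two shares add to 100% only among ICS users. The joint reading also leaves SAP 16.1.3.1 and Table 24 unmatched, so the documents conflict either way.

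Several other points stand:

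- The study is descriptive, no confirmatory test is planned, and no decision depends on ±3.2 points.
- Tables 11 and 31 already run in the right direction, SAP 8.2 makes a 95% interval the default, and Table 24 holds all four counts. What is missing is a named percentage and an interval line. No data are missing.
- Table 24's direction is useful in itself, since ICS use among non-exacerbators is the study's rationale.
- The 50% to 90% range for x is an assumption. If exacerbators used ICS far less often than non-exacerbators (x=20%), the extra half-width would be only 3.35 − 3.20 = 0.15 points.

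**Conclusion.** The concern holds. The outcome definition, the planned precision and the primary table refer to three different percentages, and no single reading reconciles all three. On the documents' figures these are about 40% (joint), 61% (Table 24, non-exacerbators) and, for the outcome as worded, 57% to 70% if ICS use among exacerbators is 50% to 90%. The arithmetic in Protocol 9.5 is correct; the denominator is the fault. The effect on precision is modest, about ±4 points against ±3.2. The larger risk is that the wrong percentage is reported as primary, with a gap of +9.3 to −4.2 points between the outcome and the Table 24 figure over that range. This should be fixed before results are reported, but it does not threaten the study. The statement about missing intervals covers only the visible shells.

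**What to change.** 1. State the denominator once, in Protocol 9.3.2.1 and SAP 16.1: FAS patients on ICS at the study visit, identified as in SAP 16.1.1.
2. In Table 24, or in Table 31 if it is named as the primary table, report within that group the percentage without and the percentage with a moderate/severe exacerbation in the previous year, each with a 95% interval. Align SAP 16.1.3.1 with this.
3. Keep the Table 24 column percentages as a display labelled secondary.
4. In Protocol 9.5 and SAP 4.2, restate the precision as about ±4 points on about 515 to 640 ICS-treated patients, and state the ICS rate in exacerbators on which that range rests (50% to 90% here).
5. Label the base of the inadequate-use row in Table 5 so that it is not taken for the primary outcome.

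The cost is one percentage and interval line, one base label and some rewording. The stated precision becomes slightly less favourable. No new data and no change in enrolment are needed.

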9.6 DATA MANAGEMENT

The data will be entered by the investigators themselves and/or authorized personnel directly in the electronic case report form (eCRF). A data management plan (DMP) will be created to describe all functions, processes, and specifications for data collection, cleaning and validation. The eCRFs will include programmable edits to obtain immediate feedback if data are missing, out of range, illogical or potentially erroneous.

AE reconciliation will be performed by the CRO, quarterly after study initiation.

When data management is outsourced, the designated contract organization will be responsible for the development and implementation of the data management plan and preparation of the data handling report according to the sponsor's standards.

The database will be housed in a physically and logically secure computer system maintained in accordance with a written security policy. The system will meet the standards of the International Committee on Harmonization guideline E6R1 regarding electronic study data handling. Patient confidentiality will be strictly maintained.

9.7 DATA ANALYSIS

Analyses will be performed by Boehringer Ingelheim's designees. The analysis population will consist of all eligible patients (i.e. all patients fulfilling all inclusion criteria and no exclusion criteria).

In this non-interventional study, retrospective data from medical charts and data at the study visit will be collected for COPD patients. Once the study has been completed and all data

from the last patient have been recorded, the database will be closed and statistical analysis will be performed.

The proposed methods for statistical analysis presented below are a summary of the methods that will be applied in the study to analyze the data collected and to answer the study objectives.

Since the study is essentially descriptive the variables included in the study objectives will be summarized by factors of interest and globally. All results will be analysed with measures of central tendency (mean and median), variability/dispersion (standard deviation and interquartile ranges), absolute and relative frequencies, and ranges. 95% confidence intervals will be provided as appropriate. The level of significance will be established at the 0.05 level (two-sided).

A Statistical Analysis Plan (SAP), will be prepared to describe all processes, treatment and specifications for data collection, cleaning, validation and analysis.

9.7.1 Main analysis

All patients who have signed the informed consent and fulfil all selection criteria will be included in the analysis. If patients have missing values for an outcome, those patients will be excluded for that outcome's analysis. Missing data will not be imputed. Number of missing values will be presented for each outcome.

Descriptive statistics will be used for describing the patient profile. All results will be analyzed with measures of central tendency (mean and median), variability/dispersion (standard deviation and interquartile ranges), distributions of absolute and relative frequencies, and ranges. 95% confidence intervals will be provided as appropriate. The level of significance will be established at the 0.05 level (two-sided).

9.7.2 Further analysis

For the secondary objectives:

Categorical variables will be analysed using Fisher's Exact test and quantitative variables by means t-test for independent groups. In case of more than two groups, One-Way ANOVA will be used and an appropriated post-hoc analysis will be done. For quantitative variables that do not meet parametric applicability criteria, adequate statistical analysis will be used, as Mann-Whitney U test or Kruskal Wallis test.

Logistic regression will be used to assess the independent contribution of clinical and demographic factors to the estimation of proportions of interest-dependent variables, such as inadequate use of ICS in patients with COPD. Additionally, multivariate logistic regression models will be used to propose estimation of proportion of these patients of interest.

Descriptive statistics will be used for describing the use of rescue medication and adverse events ICS-related.

Any update of GesEPOC /GOLD guidelines and treatment recommendations during the study will be taken into account for analysis.

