7.2.8 GOLD 2019

To determine the severity of all subjects with COPD (independently of FEV₁/FVC post-bronchodilation obtained), patients will be categorized into four levels, according to these criteria:

- Gold 1 (mild): FEV₁ (%) $\geq 80\%$ predicted.
- Gold 2 (Moderate): $50\% \leq \text{FEV}_1 (\%) < 80\%$ predicted.
- Gold 3 (Severe): $30\% \leq \text{FEV}_1 (\%) < 50\%$ predicted.
- Gold 4 (Very serious): FEV₁ (%) $< 30\%$ predicted.

In case the number of GOLD 4 subjects was less than 10, these will be grouped with the GOLD 3 subjects, forming a single category (GOLD 3-4).

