16.2.3 General patient profile for COPD patients

To evaluate general patient profile for COPD patients, several variables will be described. In general, descriptive statistics will be used for describing the patient profile. All results will be analyzed with measures of central tendency (mean and median), variability/dispersion (standard deviation and interquartile ranges and ranges) for continuous variables and distributions of absolute and relative frequencies for categorical variables. This analysis will be also performed for the FAS.

Document: \\bcnfs02\general\Hdmgener\MEDICAL AFFAIRS 28.02.2017 actualizada\8. SRO ESTUDIOS\RESPIRATORIO\1237-0070 NIS OPTI\11 - Clinical Trial Report\SAP\SAP - V 1.0\SAP OPTI version1.0 29052019.docx

Author:

Version Number: 1.0

Version Date: [29MAY2019]

Template No.: RWI_TP_BIOS0013 Revision 1

Reference: RWI_WI_BIOS0015

Effective Date: 15Jun2018

Copyright © 2018 All rights reserved. The contents of this document are confidential and proprietary to Holdings Inc. and its subsidiaries. Unauthorized use, disclosure or reproduction is strictly prohibited.

All results will be described according to the ICS treatment in the study visit: categorical variables will be analyzed using Chi-Square or Fisher’s Exact test and quantitative variables by means t-test for independent groups or for quantitative variables that do not meet parametric applicability criteria, adequate statistical analysis will be used, as Mann-Whitney U test or Kruskal Wallis test. Variables included are:

Table 2. Variables included in the eCRF

Group	Variable
Sociodemographic	Age (years),
	gender,
	ethnicity.
	BMI (Kg/m2)
	BMI grade
	Smoking history.
Clinical Variables	Spirometry - Bronchodilator test
	Spirometry - FEV1 absolute values pre and post-bronchodilator
	Spirometry - FEV1 % values pre and post-bronchodilator.
	Spirometry - FEV1 increase from pre to post-bronchodilator
	Blood Eosinophilia (number of eosinophils and %)
	Immunoglobulin E (Ig E)
Exacerbations	Episodes of exacerbations in the previous year
	Episodes of exacerbations in the two previous years
	Episodes of severe exacerbations in the previous year
	Episodes of severe exacerbations in the two previous years
	Treatments for exacerbations
COPD characteristics	Time since COPD diagnosis (years)
	COPD GesEPOC 2017 phenotypes
	GOLD 2019 spirometric classifications (Gold 1, Gold 2, Gold 3, Gold 4).
	GOLD 2019 patient groups (A, B, C, D).
	BODEx index (numerical and categories)

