COTE Index (cat)	Low risk: COTE index <4 points High risk: COTE index ≥ 4 points.			

Table 9. COPD characteristics according to current treatment on ICS.

		Non - ICS	ICS	Total
Time since COPD diagnosis (years)	Valid N Mean (SD) Median (Q1-Q3) Min-Max N missing			
Time since COPD diagnosis (cat)	0-2 years >2-5 years >5 years			
COPD GesEPOC 2017 phenotypes	non-exacerbator, mixed COPD - asthma syndrome (ACOS) exacerbator with emphysema exacerbator with chronic bronchitis			
GOLD 2019 spirometric classification	Gold 1 – Mild Gold 2 – Moderate Gold 3 – Severe Gold 4 – Very severe			
GOLD 2019 patient groups (A, B, C, D).	Patient A Patient B Patient C Patient D			
BODEx Index	Valid N Mean (SD) Median (Q1-Q3) Min-Max N missing			

Document: \\bcnfs02\general\Hdmgener\MEDICAL AFFAIRS 28.02.2017 actualizada\8. SRO ESTUDIOS\RESPIRATORIO\1237-0070 NIS OPTI\11 - Clinical Trial Report\SAP\SAP - V 1.0\SAP OPTI version1.0 29052019.docx

Author: Version Number: 1.0
Version Date: [29MAY2019]

Template No.: RWI_TP_BIOS0013 Revision 1 Reference: RWI_WI_BIOS0015

Effective Date: 15Jun2018

		Non - ICS	ICS	Total
BODEx Index (cat)	Class I Mild: BODEx 0-2 points Class II Moderate: BODEx 3-4 points Class III Serious: BODEx 5-6 points Class IV Very serious: BODEx 7-9 points			
CAT score	Valid N Mean (SD) Median (Q1-Q3) Min-Max N missing			
CAT score (cat)	CAT <10: Low impact of COPD. CAT ≥10: Medium / high impact of COPD Low impact: 0 ≤ CAT ≤ 10. Moderate impact: 11 ≤ CAT ≤ 20. High impact: 21 ≤ CAT ≤ 30. Very high impact: 31 ≤ CAT ≤ 40.			
mMRC score	Grade 0 Grade 1 Grade 2 Grade 3 Grade 4			

Table 10. Analytic results according to current treatment on ICS.

		Non - ICS	ICS	Total
Blood Eosinophilia (%)	Valid N Mean (SD) Median (Q1-Q3) Min-Max N missing			
Number of eosinophils (%)	<2% ≥ 2%			
Blood Eosinophilia (cel/μl)	Valid N Mean (SD) Median (Q1-Q3) Min-Max N missing			
Number of eosinophils (cel/μl)	<100 cel/μl 100-299 cel/μl ≥ 300 cel/μl			
Immunoglobulin E (UI/ml)	Valid N Mean (SD) Median (Q1-Q3) Min-Max			

Document: \\bcnfs02\general\Hdmgener\MEDICAL AFFAIRS 28.02.2017 actualizada\8. SRO ESTUDIOS\RESPIRATORIO\1237-0070 NIS OPTI\11 - Clinical Trial Report\SAP\SAP - V 1.0\SAP OPTI version1.0 29052019.docx

Author:

Version Number: 1.0

Version Date: [29MAY2019]

Template No.: RWI_TP_BIOS0013 Revision 1

Reference: RWI_WI_BIOS0015

Effective Date: 15Jun2018

		Non - ICS	ICS	Total
	N missing			
Inmunoglobulin E (UI/ml)	≤100 UI/ml >100 UI/ml			

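### mMRC dyspnoea grade is compared between ICS and non-ICS patients only by tests that ignore the order of the grades; for a modest one-directional shift a rank or trend test would have up to about 22 points more power

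*Protocol*

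**What the plan says.** Protocol section 9.7.2 (Further analysis) assigns tests by variable type: "Categorical variables will be analysed using Fisher's Exact test and quantitative variables by means t-test for independent groups". Rank tests appear only as a fallback for measured quantities: "For quantitative variables that do not meet parametric applicability criteria, adequate statistical analysis will be used, as Mann-Whitney U test or Kruskal Wallis test".

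SAP section 16.2.3 applies the same scheme to the patient profile by ICS use: "categorical variables will be analyzed using Chi-Square or Fisher’s Exact test and quantitative variables by means t-test for independent groups". Neither document names a trend test or any other ordinal test.

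The SAP's Table 2 (section 16.2.3) lists CAT, BODEx and COTE in both numerical and categorical form, but gives mMRC no numerical form. Table 9 (section 20.2.2) matches this. CAT and BODEx have mean and median rows as well as categories, while mMRC appears only as counts: "Grade 0 Grade 1 Grade 2 Grade 3 Grade 4". GOLD 1-4 is also shown only as categories, but FEV1 %, from which it is derived, is summarised as a quantity in Table 7.

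SAP section 7.2.8 allows for sparse data in GOLD: "In case the number of GOLD 4 subjects was less than 10, these will be grouped with the GOLD 3 subjects".

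**The concern.** An r x 2 chi-square or Fisher test gives the same p-value however the grades are relabelled. For a five-grade scale it spreads the evidence over 4 degrees of freedom, most of which describe patterns unrelated to patients being more or less breathless. If ICS users are consistently somewhat more breathless, such a test can easily miss it where a test that uses the order would not.

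CAT, BODEx and GOLD stage are largely protected because a quantitative form of each is compared by t-test or Mann-Whitney. mMRC is not, and it is one of only two measures taken from the patient at the study visit (Protocol section 9.2.3). At stake is whether the mMRC row of the profile is read as showing no difference when there is a modest, consistent one.

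**Working it through.** **The plan's own figure.** Protocol section 9.5 and SAP section 4.2 give an interval for an expected 40% with 900 patients. 0.40 ± 1.96 × √(0.40 × 0.60 / 900) = 0.40 ± 0.032, so 36.8% to 43.2%; and 900 / 0.90 = 1,000. Both reproduce. This is the precision of one proportion. The documents state no power for any between-group comparison.

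**Inputs from the documents.** N = 900 at analysis; two-sided 5% level (Protocol section 9.7); mMRC has 5 grades (4 df), GOLD has 4 stages (3 df), or 3 (2 df) if stages 3 and 4 are pooled.

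**Inputs assumed, because the documents do not give them.**
- Non-ICS distribution: mMRC 15/35/30/15/5% (alternative 20/40/25/10/5%); GOLD 15/50/28/7%, pooled 15/50/35%.
- ICS split: 560 ICS and 340 non-ICS. The documents only bound it. About 0.66 × 0.61 = 40% of all patients are on ICS without exacerbations, and the other 34% could all be off or all on ICS, so the ICS share lies between 40% and 74%.
- Shift: proportional odds, one direction.
- Patients independent. Clustering by site (about 5 patients each) is not modelled.

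**Formulas.** Let p_j and q_j be the proportions in grade j among n1 non-ICS and n2 ICS patients, b_j = (n1 p_j + n2 q_j)/N, and r_j the pooled cumulative proportion up to grade j minus b_j/2 (the midrank score).
- Chi-square: λ = (n1 n2/N) Σ (p_j − q_j)² / b_j, on (levels − 1) df.
- Rank or trend test: λ = (n1 n2/N) [Σ r_j (q_j − p_j)]² / [Σ r_j² b_j − (Σ r_j b_j)²], on 1 df.
- Power is the probability that a noncentral chi-square with that λ exceeds the central 95% point.

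The chi-square results are taken to stand for Fisher's test as well at this sample size.

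**Worked case, mMRC at odds ratio 1.4.** n1 n2/N = 340 × 560 / 900 = 211.6. The ICS distribution becomes 11.2/30.5/32.4/19.1/6.9%. Then λ = 7.35 for chi-square and 7.34 for the rank test. Almost all the signal lies in the single ordered contrast. The critical value is 9.49 on 4 df but 3.84 on 1 df, so power is 56.3% against 77.3%.

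**Power (%), chi-square v rank test, 340 v 560** (loss in points, from unrounded values):

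| Odds ratio | mMRC 0-4 | Loss | GOLD 1-4 | Loss | Loss, GOLD 3-4 pooled |
|---|---|---|---|---|---|
| 1.2 | 18.3 v 31.3 | 13.0 | 19.2 v 29.2 | 10.0 | 6.6 |
| 1.3 | 35.6 v 56.2 | 20.5 | 36.9 v 52.9 | 15.9 | 10.1 |
| 1.4 | 56.3 v 77.3 | 21.0 | 57.5 v 74.0 | 16.5 | 10.1 |
| 1.5 | 74.7 v 90.3 | 15.7 | 75.4 v 88.0 | 12.6 | 7.5 |
| 1.8 | 97.9 v 99.7 | 1.8 | 97.9 v 99.5 | 1.6 | 0.9 |

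The assumed 7% in GOLD 4 is 0.07 × 900 = 63 patients, so the pooling rule would not be triggered under that baseline. The last column only shows the effect of having fewer levels.

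**Checks.** Simulation of 4,000 mMRC tables per case gave 36.0% v 56.4% at odds ratio 1.3, 56.7% v 77.5% at 1.4 and 73.3% v 89.7% at 1.5. With no shift it gave 4.7% v 4.6%, so both tests hold their size. The alternative mMRC baseline gave 35/56/73% v 56/76/90% for the same three odds ratios. Over ICS shares of 40% to 74% the largest loss at any odds ratio was 21.6 to 21.8 points for mMRC, 16.9 to 17.0 for GOLD 1-4 and 10.4 to 10.5 for pooled GOLD. At a 74% share the mMRC loss is 10.9 points at odds ratio 1.2 and 4.2 at 1.8.

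**The opposite case.** For an assumed non-monotone difference (15/35/30/15/5% in 400 non-ICS v 20/28/27/17/8% in 500 ICS), power is 76% with chi-square and 7% with the rank test.

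**The case against.** The strongest reply is that this is a descriptive study with no stated direction. No power was planned, SAP section 8.2 treats p-values as descriptive, and the protocol's ENCePP checklist marks hypotheses to be tested as not applicable. An omnibus test is a legitimate choice for open-ended profiling, and the non-monotone example shows what is lost by replacing it. Table 9 prints every mMRC grade by ICS group and has no p-value column, so a consistent shift would be visible whatever the test. mMRC also enters the numerical BODEx index in graded form.

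Most of this stands and limits the consequence. It does not remove the gap. The SAP still assigns mMRC a test between ICS groups, and the protocol still sets a 0.05 level against which readers will judge it. BODEx mixes dyspnoea with BMI, FEV1 and severe exacerbations, so it does not isolate mMRC.

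A reader might infer three stronger things, and the documents support none of them:
- That every ordered scale loses about 20 points. GOLD 1-4 never loses more than about 17, and CAT, BODEx and GOLD each have a quantitative companion.
- That an ordered test costs nothing. The non-monotone case shows otherwise.
- That comparing severity between the groups is the study's stated objective. The primary objective describes ICS patients, and a separate secondary objective describes non-ICS patients.

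**Conclusion.** The point holds as a narrow, inexpensive improvement. The planned tests ignore order, and for mMRC nothing else in the profile analysis makes up for it. The loss peaks at about 22 points for mMRC and about 17 for GOLD 1-4, around odds ratios of 1.3 to 1.4, and shrinks for smaller and larger shifts. These sizes rest on assumed baselines, an assumed split of 900 patients, a proportional-odds shift in one direction and no clustering, so they illustrate the gap and are not properties of the plan. No estimate, confidence interval or primary result is affected.

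**What to change.** In SAP section 16.2.3, and in Protocol section 9.7.2 if it is amended, state that mMRC grade, and for consistency GOLD 1-4, BODEx class and CAT impact level, are compared between ICS groups by the Mann-Whitney test on the ordered grades or by a Cochran-Armitage trend test. Name one of the two in advance. Keep chi-square or Fisher as a labelled supplementary test for these variables and as the main test for nominal and binary variables. Keep the full grade frequencies in Table 9. If only the SAP changes, record it in SAP section 4.6, which now reports no changes from the protocol. Make the change before the between-group results are seen, or label the test post hoc.

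The cost is one sentence and a procedure option. Mann-Whitney is already in the plan and no new data are needed. The downside is low power for a non-monotone difference, which the supplementary test and the grade frequencies would still show.
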